#### Calculation

$$\begin{split} n &= Z^2 \ p \ (1-p) \ / \ L^2 \\ n &= \text{sample size} \\ Z &= \text{Confidence Interval (95\% - Z is 1.96)} \\ p &= \text{Estimated proportion of the prevalence of the condition looked for} \\ L &= \text{Range excepted} \\ n &= (1.96)^2 \ x \ 0.073 \ x \ (1 - 0.073) \ / \ (0.01)^2 = 2599.6 \end{split}$$

Corrected sample = sample size x effect of population size Sierra Leone x DEFF x (1/response rate) x (1/eligible rate)

n x (1 + (n-1)/ 7,090,000) x DEFF x (1/response rate) x (1/eligible rate)

2599.6 x 1.00 x 1.3 x 1/0.95 x 1/0.95 = 3744.6 = 3745

For this section of the household study, we aim to include 3,745 individuals. In total 1,873 household visits will be needed as we are including two randomly selected individuals per household.

#### 7.3. Sample size and sampling total

For the first part of the household survey, we need to include 10,187 individuals. The average household consists of 5.5 members; resulting in 1,852 household visits. For the second part of the survey we need less household visits as we have calculated to include 3745 individuals. These individuals are clustered as 2 per household, resulting in 1,873 household visits. Due to time and financial constraints we will maximize the household visits at 1,873. This should be sufficient for the first and second part of the survey.

A pilot study will be conducted to assess the appropriateness and utility of the design and investigate the response rate, eligible rate and use of the current small design-factor. We will also monitor the time it takes to perform the extended SOSAS repeat questionnaire. The original SOSAS questionnaire took about 30-45 minutes. In order to be successful, the new extended

questionnaire should depend on the findings of the demographics of the respondent and their surgical history and current comorbidities not last longer than 60 minutes on average.

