#### 7.2.1 Sample size survey first part

Based on the found surgical met need by Bolkan *et al.*, the expected period prevalence of major surgical procedures is 0.4% in Sierra Leone (4). This means that approximately 400 major surgeries per 100,000 population per year are performed in Sierra Leone. In the surgical volume arm, we estimate that at least twice as many minor procedures are performed. This results in an estimated prevalence (P) of major and minor surgical procedures combined of  $\pm$  1% per year. The level of precision is suggested within the range of 20% of the estimated prevalence, which allow us to apply an expected range (L) of (20% x 1% =) 0.002%.

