#### Calculation

 $\begin{array}{l} n = Z^2 \ p \ (1 - p) \ / \ L^2 \\ n = sample size \\ Z = Confidence Interval (95% - Z is 1.96) \\ p = Estimated proportion of the prevalence of the condition looked for \\ L = Range excepted \end{array}$ 

 $n=(1.96)^2 \times 0.01 \times (1-0.01) / (0.002)^2 = 9702$ 

Under the assumption that some household representatives will not consent to partake in the survey to elucidate on the surgical conditions of the other household members, we have chosen to add a margin of 5% to the sample size. Hereby we will be able to estimate the population prevalence with a reasonable precision.

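### The surgical-volume sample size omits a design effect; at the protocol's own 1% prevalence and 1.3 design effect, 1,873 households give about 22% relative precision, not 20%

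*Protocol*

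**What the plan says.** Protocol section 7.2.1 (Sample size survey first part) sizes the survey for the surgical-volume arm. It starts from 0.4% per year for major procedures and adds minor ones: "we estimate that at least twice as many minor procedures are performed". It rounds the combined prevalence to about 1%. The target is relative: "The level of precision is suggested within the range of 20% of the estimated prevalence". The resulting range is printed as 0.002%.

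The Calculation that follows uses the formula for a single proportion under simple random sampling and ends in "1-0.01) / (0.002)^2 = 9702". The only inflation is for non-consent: "we have chosen to add a margin of 5% to the sample size".

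Section 7.3 (Sample size and sampling total) carries this forward: "For the first part of the household survey, we need to include 10,187 individuals". At 5.5 members per household it derives 1,852 visits, caps visits at the 1,873 needed for the second part, and concludes: "This should be sufficient for the first and second part of the survey".

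Section 7.2.2 (Sample size survey second part) multiplies its own sample size by a design effect of 1.3. Section 7.2 says that all members of the selected households form the denominator in the first part, whereas only two per household enter the second. The Executive summary gives 75 clusters.

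**The concern.** Both parts use the same clusters and households, yet only the second is corrected for clustering. The first part takes whole households, so it has more persons per cluster, and nothing in the protocol explains why it should need no correction. Annual surgical volume is the main aim of this arm, and 20% relative precision is the only quantitative statement of how well it will be estimated. If clustering is ignored, the interval will be wider than readers are told to expect.

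The figures also contain slips of their own: the printed 9,702, the unit of the range, and the step from 0.4% plus at least twice as many to 1%. These need separating from the clustering point, because they do not all work in the same direction.

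**Working it through.** **Inputs, all from the Protocol.** Z = 1.96, p = 0.01, L = 0.002 (7.2.1, Sample size survey first part); 5% margin (same section, Calculation); 5.5 members per household and 1,873 households (7.3, Sample size and sampling total); 75 clusters (Executive summary); design effect 1.3 and 3,745 individuals (7.2.2, Sample size survey second part).

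**1. The printed figure.** n = Z² p(1−p)/L² = 3.8416 × 0.01 × 0.99 / 0.000004 = 9,507.96, so 9,508.
- The printed 9,702 is 194 higher, about 2%. It is exactly what 1.96 × 2 gives in place of 1.96²: 3.92 × 0.0099 / 0.000004 = 9,702.
- The later steps follow from it: 9,702 × 1.05 = 10,187.1, and 10,187 / 5.5 = 1,852.2.
- From 9,508 they become 9,507.96 × 1.05 = 9,983 and 9,983 / 5.5 = about 1,815.

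**2. Unit of the range.** 20% of 1% is 0.2 percentage points, which is 0.002 as a proportion. The formula uses 0.002; the text prints 0.002%.

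**3. Prevalence.** 0.4% + 2 × 0.4% = 1.2% at least, not 1%.

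**4. Persons available.** 1,873 × 5.5 = 10,301.5, or 10,301.5 / 75 = about 137 per cluster. The second part has 3,745 / 75 = about 50 per cluster.

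**5. Precision without clustering.** Relative half-width = 1.96 × √(DEFF × p(1−p)/n) / p. With DEFF 1, p = 1% and n = 10,301.5 this is 19.2%. The target is met, and the design effect can rise to 10,301.5 / 9,507.96 = about 1.08 before it is missed.

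**6. Precision with the protocol's own 1.3.** At p = 1% the half-width is 0.219 percentage points, or 21.9% relative. Meeting 20% needs 9,507.96 × 1.3 = 12,361 persons; with the 5% margin 12,979, and 12,979 / 5.5 = about 2,360 households. Without the margin it is 12,361 / 5.5 = about 2,248, still above the cap.

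**7. A larger design effect, as an assumption.** The protocol gives no intracluster correlation for this outcome. If the second part's 1.3 at about 50 per cluster is read as a correlation of 0.3 / 48.93 = about 0.006, the same value at about 137 per cluster gives 1 + 136.35 × 0.00613 = about 1.84.

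**8. Expected relative precision at 1,873 households**

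| Prevalence | DEFF 1.3 | DEFF 1.84 (assumed) |
|---|---|---|
| 1% (protocol) | 21.9% | 26% |
| 1.2% (implied by the text) | 20.0% | 24% |
| 0.4% (major only, no target set) | 35% | 41% |

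At 1.2% and DEFF 1.3: 3.8416 × 0.012 × 0.988 / 0.0024² = 7,907; × 1.3 = 10,279 against 10,301.5 available, which is 19.98%.

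**The case against.** The best defence is that the shortfall is small and depends on the inputs. If p is taken as 1.2%, as the protocol's own reasoning implies, and the design effect as 1.3, the target is just met at 19.98%. This stands, with two qualifications. The protocol chose 1% and draws its conclusion at that value. The margin at 1.2% is also negligible, and it assumes that L is rescaled to 0.24 points; if L stayed at 0.2 points, simple random sampling alone would need 3.8416 × 0.012 × 0.988 / 0.002² = 11,387 persons.

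It is also fair that the precision target is worded softly, that the arm is descriptive with no hypothesis test, and that visits are capped for time and cost. Refusing or empty households are replaced, so non-response need not widen the gap. Section 7.3 further promises a pilot that will look at the small design factor, but that factor appears only in the second part, so there is no value for the first part to revisit.

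Three stronger readings are tempting and not supported:
- A reader might infer that the wrong 9,702 is why 20% is not reached. It errs upwards; correcting it lowers the requirement to about 1,815 households, and without clustering the cap gives 19.2%.
- A reader might take 24–26% as the expected precision. Those figures need a design effect of 1.84, back-solved from a value assumed for a different outcome.
- A reader might say that major procedures miss the 20% target. That target was set for major and minor procedures combined.

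**Conclusion.** The point holds in a limited form. The first part has no design effect, and at the protocol's stated p = 1% with its own 1.3, the 1,873-household cap gives about 22% relative precision against a stated 20%. The sufficiency statement in section 7.3 is therefore unsupported at the stated inputs. The gap is about two percentage points of relative precision. It closes, barely, at p = 1.2% with 1.3, and widens to about 24–26% only under the assumed design effect of 1.84. The shortfall rests on the missing design effect alone.

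The slips in 9,702, 10,187, 1,852 and 0.002%, and the mismatch between 1% and 1.2%, are real but separate. None changes the fieldwork, because the second part already fixes 1,873 households.

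For major procedures alone, only about 41 events are expected (10,302 × 0.004). Their precision of roughly 35% at 1.3, or 41% at 1.84, is worth stating for information, since 0.4% is the 2012 figure that this arm starts from.

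**What to change.** In section 7.2.1 (Sample size survey first part) and its Calculation:
- Replace 9,702 with 9,508, and print the range as 0.002, that is 0.2 percentage points.
- Either use 1.2% or explain why 1% is kept, and rescale the range if the prevalence changes.
- State a design effect for this part and the reason for the value, noting about 137 persons per cluster.

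In section 7.3 (Sample size and sampling total):
- Replace 10,187 and 1,852 with about 9,983 and about 1,815, described as the requirement before any design effect.
- Keep 1,873 households. Replace the sufficiency statement for the first part with the expected relative precision as a range: about 22% at p = 1% and about 20% at p = 1.2% with design effect 1.3; about 26% and 24% if 1.84 is assumed.
- Add that major procedures alone, for which no target is set, would have about 35% (1.3) to 41% (1.84).
- Say that the pilot's review of the design factor also covers the first part.

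The cost is a change of wording and a less favourable stated precision. No households are added.

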#### 7.2.1. Sampling method for the clusters

Sierra Leone is divided in four provinces, further divided into 16 districts, and 190 chiefdoms, which are further divided into 9,671 enumeration areas, the smallest administrative units in Sierra Leone. Sampling will be done through a weighted random cluster design, where the probability of cluster choice is proportional to the population size. From this moment onwards, a cluster and an enumeration area are the same. For Sierra Leone, the clusters will be randomly chosen in a two-stage sampling process starting with the Chiefdoms and selecting the number of clusters needed out of the Chiefdoms proportional to the population size in the chiefdoms to further select, the Enumerator Areas (EA's) out of the Chiefdoms. This process of sampling will be led by Statistics Sierra Leone, who will also provide maps and coordinates for the assigned clusters.

#### 7.2.2. Assignment of the households within the cluster

If maps of structures of the randomly selected EAs are available, those are used for randomly designing the first household to approach. Thereafter every fifth structure at the right side of the interviewed household while standing with the back to the front door is approached for the survey. In case of more households per structure an on-site listing is made and random assignment of the household is facilitated by the use of the random calculator (that will be available on the tablet). If maps of structures are not available or out-dated an onsite structure count is made and random assignment of structures is given, by utilizing a random calculator.

To be able to have a weighted cluster sample, each cluster should have the same household numbers interviewed. Therefore, if a structure randomly chosen appears to be empty or the household does not give informed consent the next structure will be approached to be interviewed. Records will be kept on households' and individuals' refusal to participate, for the analysis of the results.

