#### Methods

Cross-sectional study using a national community-based sampling survey to estimate surgical need in Sierra Leone. We will randomly select 1,873 households from 75 nationwide representative clusters. Sampling will be done through a weighted random cluster design, where the probability of cluster choice is proportional to the population size. Sampling of the individuals in the households starts after the determination of the household size/household denominator. A random number calculator will assign two household members to be surveyed using the SOSAS repeat questionnaire. For this study purpose, the SOSAS questionnaire is complemented with additional questions on groin hernia and wounds. Furthermore, if a selected household member is a male over the age of 12 years, or the randomly selected individuals are females in their reproductive years; the SOSAS repeat survey will be further extended with questions regarding LUTS or maternal health respectively. In contrary to the original SOSAS study, all household members of the randomly selected ménage will be asked to participate in the surgical volume arm if they have had a surgical procedure in the past year.

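### Within an enumeration area, a household in a shared structure has about 1/h the chance of one living alone (h = households in the structure), and the protocol does not say that h is kept

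*Protocol*

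**What the plan says.** Clusters, which are enumeration areas (EAs), are chosen as follows: "Sampling will be done through a weighted random cluster design, where the probability of cluster choice is proportional to the population size" (Protocol, Sampling method for the clusters). The executive summary gives the scale: "We will randomly select 1,873 households from 75 nationwide representative clusters", or about 25 households per cluster.

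Inside an EA, the section Assignment of the households within the cluster gives two routes:

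- **Usable maps:** a random start, then "Thereafter every fifth structure at the right side of the interviewed household while standing with the back to the front door is approached".
- **No usable maps:** "an onsite structure count is made and random assignment of structures is given, by utilizing a random calculator".

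On either route, a structure with several households is handled thus: "In case of more households per structure an on-site listing is made and random assignment of the household is facilitated". The replacement rule also works on structures: "if a structure randomly chosen appears to be empty or the household does not give informed consent the next structure will be approached".

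The equalising device named is: "To be able to have a weighted cluster sample, each cluster should have the same household numbers interviewed". The records that this section names for the analysis are: "Records will be kept on households' and individuals' refusal to participate, for the analysis of the results". It does not mention keeping the number of households found in a structure.

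**The concern.** The survey is meant to represent households and the people in them, but the unit drawn with roughly equal chance inside an EA is the building. Picking one household at random in a shared building divides that household's chance by the number sharing. Equal numbers of interviews per cluster balance the sample between EAs and leave the imbalance inside an EA as it was.

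At stake are the prevalence estimates wherever people in shared and single structures of the same EA differ in surgical conditions. Timing matters too. An analysis plan can correct for unequal selection only if h was stored. The listing that yields h is made in the field, and if it is not captured there it cannot be recovered later. This is a separate mechanism from the replacement of empty or refusing households, and from interviewing two people whatever the household size.

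**Working it through.** **The plan's own figure.** With p = 0.073 and L = 0.01, n = 1.96² × 0.073 × 0.927 / 0.01² = 2,599.6. Then 2,599.6 × 1.3 / 0.95 / 0.95 = 3,744.6, so 3,745 individuals and 1,873 households. This reproduces. Per cluster, 1,873 / 75 = 24.97 households. The design effect (DEFF) of 1.3 is justified by clustering alone.

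**Selection chance.** With m of M structures drawn in an EA and one household taken from a structure of h:

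P(household | EA) = (m/M) × (1/h).

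Example: 200 structures, 60 with three households, 25 drawn. A household living alone has 25/200 = 0.125; one in a three-household structure has 0.125/3 = 0.0417. A simulation gave the same ratio of 3.0. Neither the cluster selection nor the fixed take enters this ratio.

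**Size of bias, on assumed inputs.** The protocol gives neither the share of shared structures nor h. Assume nationally that s = 20% of structures hold h = 3 households. Their share of all households is s·h / (s·h + 1 − s) = 0.6 / 1.4 = 0.429. The unweighted bias is (true share − sampled share) × prevalence difference. The take per EA is fixed and household size is assumed alike across EAs.

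| Where the shared structures lie | Sampled share | Gap | Bias at a 5-point difference |
|---|---|---|---|
| Same mix in every EA | 0.200 | 0.229 | 1.1 points |
| Only in EAs holding half of all households | 0.333 | 0.095 | 0.48 points |
| Only in EAs where every structure holds three | 0.429 | 0 | 0 |

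Middle row: in those EAs 0.429 / 0.5 = 0.857 of households are shared. By structure that is (0.857/3) / (0.857/3 + 0.143) = 0.667. Nationally the sampled share is 0.5 × 0.667 = 0.333.

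**How large is 5 points?** Around an overall 7.3% it means 7.3 − 0.429 × 5 = 5.2% in single structures and 10.2% in shared ones, nearly double. With a 1.5-fold ratio instead, single structures have 7.3 / (1 + 0.5 × 0.429) = 6.0% and the difference is 3.0 points. The first two rows then give 0.229 × 3.0 = 0.69 and 0.095 × 3.0 = 0.29 points.

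**Cost of weighting by h.** The Kish factor is E[w²] / E[w]² over the sample, with the same mix in every EA:

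- s = 0.2, h = 2: (0.2 × 4 + 0.8) / 1.2² = 1.11
- s = 0.2, h = 3: (0.2 × 9 + 0.8) / 1.4² = 1.33
- s = 0.5, h = 4: (0.5 × 16 + 0.5) / 2.5² = 1.36

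If these multiply the planned variance, the 1-point range widens by √1.11 to √1.36, to between 1.05 and 1.17 points.

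**When weighting pays.** The planned standard error is 1/1.96 = 0.51 points. For s = 0.2, h = 3 and the same mix everywhere, the added variance is 0.51² × 0.33 = 0.085. This equals the squared bias when 0.229 × d = √0.085 = 0.29, so d is about 1.3 points. Above that difference, weighting lowers the mean squared error.

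**The case against.** The strongest objection is that cluster selection already protects what matters most. EAs are taken in proportion to population with a fixed number of households, so dense urban EAs keep about their proper share however many households share a building. Distance to hospital and private provision vary mainly between EAs, which average only 7,090,000 / 9,671 = about 733 people. This stands. A reader might infer that urban areas are under-sampled and that the public/private split is distorted as a result; the document does not support that. The more the shared structures are concentrated in particular EAs, the smaller the bias, as the table shows.

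It also stands that 1.1 points is the top of the range for that scenario and not a central value, and that a 5-point difference is large against 7.3%. For the surgical-volume rate, planned at about 1%, such a difference is implausible, and no figure is supported for that arm.

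Three limits concern the reading of the text:

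- One household per structure is inferred from the singular noun and the replacement rule. The section on sampling individuals speaks of the next household where neither selected member takes part. No text provides for taking several households from a structure.
- On the map route, equal chance per structure is only approximate.
- The questionnaire is a separate document and the field handbook was still to be finalised, so h may already be captured. A reader might infer that the count is discarded; the protocol says only that the listing is made.

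If the 2012 survey used the same rule, some bias may cancel in that comparison, but not in the absolute prevalences.

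None of this removes the 1/h ratio inside an EA with both kinds of structure.

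**Conclusion.** The point holds as a within-EA selection problem. Followed as written, the rule gives households in shared structures about 1/h the chance of sole occupants, and the equal take per cluster does not repair it. Whether this biases a result depends on shared and single structures differing in prevalence inside the same EA, for which the protocol gives no evidence either way.

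The size is therefore conditional. With 20% of structures holding three households and a 5-point difference, it lies between 0 and about 1.1 points, against a planned range of 1 point. Smaller differences give proportionately less. It is worth fixing because the remedy is cheap and has to be in place before fieldwork. It does not show that the planned estimates are wrong by any particular amount. If the questionnaire already stores the number of households per structure, only the weighting remains to be stated.

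**What to change.** Record in REDCap the number of households listed in every sampled structure, entering 1 where there is only one. State in the protocol that one household is taken per structure.

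Weight each interviewed household by h, scaled so that the weights sum to the same total in every EA, for example w = 25·h / Σh over the interviewed households of that EA. Raw h would over-weight EAs where most structures are shared and undo the balance that the cluster selection provides. Set a cap on the weights in advance and report an unweighted sensitivity analysis.

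The cost is one data field, taken from a listing that is already made, and a variance increase of about 11% to 36% in the assumed scenarios. That increase should be stated next to the DEFF of 1.3. The planned pilot, which is to examine the design factor anyway, can supply the actual distribution of h.

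Drawing from a full household list of the EA would remove the problem at source, but it adds field work and is optional.
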